7.3 Statistical Analysis

In order to assess whether PK steady state has been approximately achieved, descriptive statistics for trough (Cmin) measurements of plasma lithium and Cmax (peak) measurements of plasma salicylate will be presented for all available days by cohort and overall. In addition, these measurements for plasma lithium and salicylate on Days 13 and 14 for each cohort will be \log^e -transformed and a 90% CI for the difference in the measurements between Days 13 and 14 for lithium and salicylate will be calculated on the \log^e scale and then transformed back to the original scale for each cohort. If the 90% CI on the original scale is contained within the interval 85.0% to 117.6%, then an approximation of steady state will be concluded for the respective analyte and cohort. Alternative approaches to estimate achievement of steady-state conditions are to be used, as appropriate, such as when at least 3 trough concentrations for plasma lithium and/or at least 3 Cmax concentrations for plasma salicylate can be assessed using linear regression. All cohorts except Cohort 1 are expected to complete at least 3 lithium trough and 3 salicylate peak concentration measurements and should be candidates for this statistical approach.

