2 STUDY OBJECTIVES

The objectives of the study and corresponding study endpoints are detailed in Table 1.

Table 1: Objectives and Related Endpoints

Objective	Endpoint	Analysis
Primary		
To evaluate the safety and tolerability of AL001 under multiple-dose, steady-state conditions in Alzheimer's subjects and healthy adult subjects.	
 • Vital signs (blood pressure, heart rate, and oral body temperature) • 12-lead electrocardiogram • Physical examination • Safety laboratory tests (hematology, chemistry [including thyroid-stimulating hormone (TSH), vitamin B12, and Mg], HbA1c, and urinalysis • Reported and observed Adverse events (AEs)/serious AEs)/tolerability observations including signs and/or symptoms of lithium and/or salicylate toxicity 	Refer to Section 8
Secondary		
To characterize the Maximum tolerated dose (MTD) of AL001 in patients with mild to moderate Alzheimer's disease (AD) and healthy adult subjects.	
 • Prevalence of peak salicylate concentrations above 30 mg/dL • Prevalence of trough plasma lithium concentrations above 1.2 mEq/L for healthy adult subjects or 1.0 mEq/L for healthy elderly and Alzheimer's subjects. 	Refer to Section 7
Exploratory		
To explore the difference in PK profile between the non-elderly vs elderly subjects (healthy subjects only).	
 • Descriptive statistics for PK will be presented by treatment group and compared between non-elderly and elderly subjects. 	Refer to Section 7

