3 STUDY DESIGN

3.1 General Description

This is a Phase 1/2a, multi-center, double-blind, placebo-controlled, randomized, MAD clinical study to determine the safety and MTD of AL001 in subjects with mild to moderate AD (FDA Classification of Stage 2 to 4 AD [protocol APPENDIX 3]) and healthy adult subjects. Cohorts 1, 2b, 3b, 4b, and 5b will include AD subjects (between the ages of 50 and 80 years, inclusive) and Cohorts 2a, 3a, 4a, and 5a will include healthy subjects (non-elderly adults between the ages of 18 to 64 years, inclusive, and healthy elderly adults between the ages of 65 to 80 years, inclusive). In each of the 9 cohorts, subjects will be confined to the study site from Day -1 until Day 15.

The study consists of 3 phases.

1. Screening Phase – up to 28 days (from Days -28 to -1)
2. Treatment Phase – 16 days:
 - Subjects will be admitted to the study site on Day -1. Subjects will receive 14 days of 3 times daily (TID) dosing with assigned study medication from Days 1 to 14 and will remain confined until Day 15.
 - Each of the 9 cohorts will be initiated sequentially starting with Cohort 1 and progressing through to Cohort 5 depending on acceptable review of the safety data by a 3-member expert adjudication panel. Each of the Cohorts 2 to 5 will be subdivided into 2 cohorts: Cohorts 2a, 3a, 4a, and 5a will include healthy subjects and Cohorts 2b, 3b, 4b, and 5b will include AD subjects. The results from the healthy subject cohorts ‘a’ will be reviewed by the independent safety adjudication committee and if assessed as safe, the committee will permit progression to the corresponding AD subject cohort ‘b’ at the same dose level, as well as progression to the next dose level of healthy subject cohort. The healthy subject cohorts can proceed to the next higher dose level without having to wait for the corresponding AD subject cohort to be completed and reviewed by the safety adjudication panel.
 - The initiation of the next dose cohort may be delayed up to approximately 4 weeks following the last dose of the last subject in the preceding cohort. This is necessary to allow time for the safety and PK data to be compiled and tabulated for review by the safety committee (laboratory reports, AEs, tolerability, and PK data from all [up to 8] completed subjects in each cohort), to determine if it is safe to proceed with enrollment of the subsequent cohort.
3. Follow-up Phase - 1 month

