⁶ Blood samples for baseline plasma lithium and plasma salicylate concentration measurements will be collected before first dose on Day 1. Blood samples for trough plasma lithium and peak plasma salicylate concentration measurements will be collected on Days 3, 5, 7, 10, 13, and 14, and at the discretion of the Investigator (the latter are 'Safety Samples' for Therapeutic Drug Monitoring), particularly to assess the relationship to possible lithium or salicylate related AEs. These safety samples could be sent for expedited analysis to either a local laboratory with an aliquot saved for the bioanalytical laboratory, or to the bioanalytical laboratory directly (Sannova or Altasciences). In addition, for AD subject Cohorts 2b, 3b, 4b, and 5b, the trough lithium sample on Day 5 will be treated as a 'Safety Sample' for Therapeutic Drug Monitoring to assess any lithium-related PK exposure safety concerns at an early treatment time point which may require dosing to be discontinued for an individual subject. This sample will be sent to Sannova for expedited analysis. Similarity between Days 13 and 14 trough lithium plasma levels and peak salicylate plasma levels will be used to determine the status of lithium and salicylate steady-state PK conditions, and/or by another appropriate method, such as linear regression. Blood collection for trough lithium plasma concentrations will occur just prior to the first daily dose, while blood collection for peak plasma salicylate concentrations will occur at 1.25 hours post third daily dose (the estimated time to a maximum blood concentration C_{max}). For early termination, blood samples for lithium and salicylate plasma concentrations will be collected. A ±10-minute window will be allowed for collection of PK samples for both lithium and salicylate.

⁷ Hachinski Ischemic Scale Score is presented in protocol APPENDIX 5.

Study Procedures	Screening (28 days prior to randomization)	In-patient admission	Treatment Period		Clinic Discharge	Follow-up Period		Early Termination (ET)
Study Day	Days -28 to -1	Day -1	Day 1	Days 2 to 14	Day 15	Day 23 ±1 day Clinic Visit	Day 42 ±2 days Telephone call	
Adverse Event Reporting/Safety-Tolerability Assessment	X	X	X	X	X	X	X	X
Prior Medications	X	X						
Concomitant Medications	X	X	X	X	X	X	X	X
Health Status Questionnaire (SF-36)						X	X	X

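### The Day 13 versus Day 14 steady-state rule is nearly uninformative: under fixed dosing and constant elimination the true ratio cannot exceed 1.083, well inside the 85.0–117.6% limits

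*SAP*

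**What the plan says.** The primary objective (SAP section 2, Table 1) is "To evaluate the safety and tolerability of AL001 under multiple-dose, steady-state conditions". Section 7.3 is where the plan decides whether those conditions were approximately reached. Day 13 and Day 14 values are log-transformed and a 90% confidence interval for their difference is back-transformed, for each cohort and analyte. The rule then reads: "If the 90% CI on the original scale is contained within the interval 85.0% to 117.6%, then an approximation of steady state" is concluded. Appendix A, footnote 6, gives the comparison the same role: "Similarity between Days 13 and 14 trough lithium plasma levels and peak salicylate plasma levels will be used to determine the status" of steady state for both analytes.

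The schedule is fixed. Section 3.1: "Subjects will receive 14 days of 3 times daily (TID) dosing with assigned study medication from Days 1 to 14". Appendix A, footnote 6: "Blood samples for trough plasma lithium and peak plasma salicylate concentration measurements will be collected on Days 3, 5, 7, 10, 13, and 14". For lithium, "Blood collection for trough lithium plasma concentrations will occur just prior to the first daily dose"; the salicylate peak is drawn 1.25 hours after the third daily dose.

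The plan also contains two softer elements. Descriptive statistics for troughs and peaks "will be presented for all available days by cohort and overall", and "Alternative approaches to estimate achievement of steady-state conditions are to be used, as appropriate", with linear regression on at least three samples given as the example. Neither has a decision criterion, and the SAP does not say which method prevails if they disagree. Section 7.3 appears twice in the supplied SAP text with the same wording.

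**The concern.** A steady-state test should be able to fail when drug is still accumulating. Two adjacent days late in a fixed regimen differ by only one day's dosing in thirteen or fourteen, so the true ratio is close to 1 whether or not a plateau has been reached. If no plausible degree of accumulation can move the true ratio outside the limits, a pass shows mainly that the data were precise, and a fail shows mainly that they were not.

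What is at stake is the steady-state wording of the primary objective and of the study title. A reported pass would naturally be cited in support of it, and a fail could be misread as evidence that the plateau was not reached.

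**Working it through.** **Limits.** 1/0.85 = 1.1765, so 85.0% to 117.6% is a symmetric interval on the log scale. The plan's figure reproduces.

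**Doses before each sample** (three per day from Day 1; SAP 3.1 and Appendix A, footnote 6):

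- Lithium trough, before the first dose of the day: Day 13, 12 × 3 = 36; Day 14, 13 × 3 = 39.
- Salicylate peak, after the third dose: Day 13, 13 × 3 = 39; Day 14, 14 × 3 = 42.

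**Largest possible true ratio.** With identical daily doses and a constant elimination rate k per day, the level after m dosing days is proportional to 1 − exp(−km).

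- Lithium: (1 − exp(−13k))/(1 − exp(−12k)), which rises to 13/12 = 1.083 as k goes to 0.
- Salicylate: (1 − exp(−14k))/(1 − exp(−13k)), which rises to 14/13 = 1.077.

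Numerical checks with the actual clock times, first-order absorption and saturable elimination gave at most about 1.083 (trough) and 1.079 (peak).

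**Lithium by assumed half-life** (the documents give none):

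| Half-life | Share of plateau at Day 14 trough | Day 14/Day 13 |
|---|---|---|
| 2 days | 99% | 1.005 |
| 3 days | 95% | 1.014 |
| 10 days | 59% | 1.052 |
| 13 days | 50% | 1.058 |
| No elimination | 0% | 1.083 |

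**Probability of concluding steady state.** Assumptions: n = 6 active subjects (SAP 3.5), a paired interval, and σ_w = √ln(1 + CV²), so the SD of a paired log difference is √2·σ_w. The interval half-width is t(0.95, 5)·√(2/6)·s_w = 2.015 × 0.577 × s_w = 1.163·s_w. The half-width of the limits is (ln 1.176 − ln 0.85)/2 = (0.1621 + 0.1625)/2 = 0.1623. Even a perfectly centred interval therefore needs s_w below 0.1623/1.163 = 0.140. Integrating over the chi-square distribution of the variance gives, for lithium:

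| Within-subject CV (assumed) | At plateau | 10-day half-life | No elimination |
|---|---|---|---|
| 5% | >0.99 | 0.95 | 0.79 |
| 8% | 0.83 | 0.66 | 0.45 |
| 10% | 0.58 | 0.46 | 0.32 |
| 20% | 0.050 | 0.045 | 0.040 |

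Salicylate with no elimination passes 0.83 of the time at CV 5% and 0.50 at CV 8%. The chance that the interval is too wide to fit wherever it is centred is 8% at CV 10%, 50% at CV 15% and 78% at CV 20%. Cohort 1 appears to have 7 active subjects (14.3% with adverse events in the synopsis is 1/7). With n = 7, lithium with no elimination passes 0.86 at CV 5% and 0.52 at CV 8%.

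**The same test on Day 14/Day 10.**

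- No elimination: 13/9 = 1.44 (lithium), 14/10 = 1.40 (salicylate).
- 10-day half-life: 1.28 and 1.24.

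All four lie outside 1.176. Over CV 5–20%, the false-pass rate at a 10-day half-life is at most 0.006 (lithium) or 0.012 (salicylate). With no elimination it is at most 0.0004 or 0.001. Pass rates at plateau are the same as under the present rule, given equal within-subject variability on the days compared. The true ratio reaches 1.176 at a half-life of about 5.1 days for lithium (83% of plateau) and 6.2 days for salicylate (79%).

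**The case against.** The strongest reply is that the plan does not rest on this test alone. Section 7.3 begins with descriptive statistics over all sampled days, the Day 13/14 interval is an addition, and regression is offered, with every cohort except Cohort 1 expected to have enough samples. Gross accumulation would be visible in that output. This is fair, and it limits the harm. It does not rescue the rule: only the interval leads to a stated conclusion, and nothing says what regression result would count against steady state.

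Second, nothing downstream depends on the conclusion, and Day 14 may well be near plateau; half-lives of 2–3 days give 99–95%. Both points stand. The problem is that the test could not show it, not that steady state was missed.

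Third, the rule has some discrimination at moderate CVs (0.83 against 0.45 at CV 8%), and it could detect a late fall in clearance, which the bound excludes. Both are true, which is why the rule is called nearly, and not wholly, uninformative.

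Fourth, the SAP does not say that the interval is paired. An unpaired interval would add between-subject variability and make failure more likely whatever the true ratio. The pass rates would change; the 1.083 bound would not.

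Finally, a Day 14/Day 10 rule avoids false passes largely by withholding a verdict. For lithium at a 10-day half-life it would declare steady state not reached 0.35 of the time at CV 10% and 0.16 at CV 20%, with most of the rest inconclusive. That is a real limit of six subjects per cohort, and an honest inconclusive result is better than an uninformative pass.

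**Conclusion.** The concern holds. Under constant dosing, complete dose-taking, zero baseline and elimination that does not change over time, no accumulation state can put the true Day 14/Day 13 ratio outside 85.0–117.6%. That part needs no outside figure. The pass rates do rest on assumptions: CVs of 5–20%, half-lives up to the no-elimination limit, six subjects and a paired interval. Across that range the outcome is driven more by precision than by accumulation: 0.79 for lithium with no elimination at CV 5%, against 0.05 at true plateau with CV 20%.

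The weight is moderate. The rule is the only stated criterion for the steady-state condition in the primary objective, but no endpoint, analysis set or escalation step in the supplied text uses it. The supplied protocol document is a study-report synopsis. The full protocol version 8.0, on which the SAP is based, was not available and could contain more.

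**What to change.** In section 7.3, replace the Day 14/Day 13 contrast with Day 14/Day 10 as the decision rule, keeping the 90% interval, the limits and the conclusion per analyte and cohort. State that the interval is paired within subject. Define three outcomes: interval inside the limits, approximate steady state; interval wholly outside, not at steady state; otherwise, inconclusive. Keep Day 13 versus Day 14 and the regression as descriptive. Report Cohort 1 descriptively if it has no Day 10 sample.

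If cohorts are modelled together for precision, include a cohort-by-day term and report each cohort's ratio and interval. A common day effect should be supportive only: with one no-elimination lithium cohort among seven (42 paired differences, 6 shifted by ln(13/9)), the pooled interval still passes 0.75 of the time at CV 20% and more than 0.99 at CV 10%.

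The cost is one paragraph and one contrast per analyte and cohort, with no new samples. There are three drawbacks:

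- The study was completed on 2023/05/15, so the analysis must be labelled post hoc.
- At CV 15–20% most single cohorts will be inconclusive, as few would pass now (plateau pass rates 0.17 and 0.05 under either contrast).
- The new contrast is stricter just short of plateau. At a 3-day half-life lithium passes 0.76 instead of more than 0.99 at CV 5%, and 0.44 instead of 0.81 at CV 8%. At a 2-day half-life it passes 0.98 and 0.75.

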8 SAFETY ANALYSIS

Unless otherwise specified, all available data will be listed and summary tables for safety assessments will be presented by treatment (dose level of AL001 and pooled placebo) per cohort for the safety population as detailed in Table 5 and all applicable safety data will be presented by combined active and pooled placebo groups, such as, disposition, demographic, adverse events, labs, vital signs, and 12-ECG data.

Continuous variables will be summarized (absolute values and change from baseline) using descriptive statistics (n, mean, SD, minimum, median and maximum).

Table 5: Data Presentations for Safety Assessments

Data	Variables	Presentation
Adverse events	Adverse event (AE) description, date and time (start and end), intensity, relationship to study drug, action taken, study days and outcome	Listing Table
Extent of exposure	Study drug administration dose, units, date, time, cohort	Listing
Clinical laboratory evaluations	Laboratory results (refer to section 8.3 for parameters)	Listing Table
Vital signs	Blood pressure, pulse, and body temperature	Listing Table
Physical examinations	Physical examinations findings	Listing
12-Lead ECGs	ECG interpretations and findings	Listing Table

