
Summary - Conclusions
 
Pharmacokinetic Results:
 
The observed AL001 MTD (the Cohort 4a/4b dosing level, 1680 mg given TID at 8 AM, 2 PM, and 8 PM, total daily dose 5040 mg) provided lithium at a lithium carbonate equivalent dose of 240 mg TID (720 mg daily) or a lithium citrate oral solution or syrup (8 mEq/5 mL) equivalent dose of 4 mL TID (19.2 mEq daily), all under fasted conditions. With respect to salicylate, these levels of exposure can be justified as safe a posteriori since they are less than the maximum for prescriptive aspirin/salicylate indications and are to be used for a serious medical condition. There were no undue safety concerns identified in the AL001-ALZ02 Study and so none were considered to be related to PK exposures. The MTD was selected to mitigate or obviate the need for AL001 therapeutic drug monitoring (TDM) in targeted neurodegenerative, neurological, and neuropsychiatric conditions, at least for subjects without undue renal compromise.
 
Under the conditions of this study, no clinically obvious or relevant lithium or salicylate PK differences were observed between non-elderly and elderly healthy subjects.
 
There were no obvious demographic characteristics observed under the conditions of this study that can be used to improve future enrollments when screening subjects.
		

Safety Results:

AD Subject Cohorts

- No deaths or SAEs occurred during the study. No subject prematurely discontinued the study due to a treatment-emergent AE (TEAE).
- AL001 was well tolerated in AD subjects regardless of their comorbidities and concomitant medications.
- A total of 24 TEAEs were experienced by 12 of 25 subjects who received AL001 and 6 TEAEs were experienced by 4 of 8 subjects in the pooled placebo group. The proportion of AD subjects with TEAEs increased with increasing dose levels of AL001, with the lowest proportions of subjects in Cohorts 1 (14.3%; AL001 1890 mg) and 2b (16.7%; AL001 3150 mg), and the highest proportion observed (83.3%) in Cohorts 3b (AL001 4410 mg) and 4b (AL001 5040 mg). The proportion of subjects with TEAEs in the pooled placebo group (50.0%) was between that observed in AL001 Cohorts 2b and 3b.
- All TEAEs were experienced by only 1 subject who received either AL001 or placebo, except headache (1 of 6 subjects [16.7%] each in Cohorts 3b and 4b) and pollakiuria (2 of 6 subjects [33.3%] in Cohort 4b).
- No AEs of special interest were reported for AD subjects.

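### Does the combined-active safety column hide a rise in adverse events with dose?

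*SAP*

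**What the plan says.** SAP Section 8 sets the safety presentation in one sentence with two parts. The first part requires summary tables by treatment, meaning each AL001 dose level and pooled placebo, per cohort. The second adds that "all applicable safety data will be presented by combined active and pooled placebo groups", and names disposition, demographics, adverse events, laboratory data, vital signs and ECG.

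Section 8.1 builds the overall TEAE summary, including drug-related TEAEs, with columns for each dose level, pooled placebo and overall. Sections 8.3, 8.4 and 8.6 do the same for laboratory data, vital signs and ECG. Section 9.1 gives summaries by cohort and dose level as the general rule and presents combined active as a further display. The SAP text appears twice in the file. Sections 8 and 9.1 of the second copy keep the dose-level tables and have no combined-active display.

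No confidence interval, trend test or dose-response model is specified for any safety variable. In SAP Table 1 the endpoints under the maximum tolerated dose (MTD) objective are concentrations only: "Prevalence of peak salicylate concentrations above 30 mg/dL" and the matching lithium trough thresholds.

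The Protocol synopsis (Safety Results, AD cohorts) reports that "A total of 24 TEAEs were experienced by 12 of 25 subjects who received AL001" and that "6 TEAEs were experienced by 4 of 8 subjects in the pooled placebo group". It then states: "The proportion of AD subjects with TEAEs increased with increasing dose levels of AL001".

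**The concern.** An ascending-dose study asks how tolerability changes with dose. A single active column averages over the variable under study. In the AD cohorts the effect is striking: two low rates and two high rates merge into 48.0%, which no dose group showed and which sits next to a placebo rate of 50.0%. If that column were the main safety comparison, a reader would see no difference from placebo while the rate at the two higher doses was about five times that at the two lower ones.

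Two further features add to the impression. No interval or trend estimate is planned for the dose-level cells. The MTD endpoints are exposure thresholds, so adverse-event rates by dose are not listed under that objective. The primary objective is safety and tolerability, and the report concludes that AL001 was well tolerated, so a masked dose relation would be serious.

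**Working it through.** **Inputs** (Protocol synopsis, Safety Results, AD cohorts)
- AL001 overall 12 of 25; pooled placebo 4 of 8.
- Cohort 1 (1890 mg/day) 14.3%; Cohort 2b (3150 mg/day) 16.7%; Cohorts 3b (4410 mg/day) and 4b (5040 mg/day) 83.3% each.

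**1. Reproduce the reported counts.** For group sizes of 5 to 8, the only fractions that round to these percentages are 1/7, 1/6, 5/6 and 5/6. Their sum is (1 + 1 + 5 + 5)/(7 + 6 + 6 + 6) = 12/25, as reported.

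**2. Pooled against by dose.**
- Combined active: 12/25 = 48.0%. Placebo: 4/8 = 50.0%. Difference −2.0 points, Fisher exact p = 1.00.
- Two lower doses: 2/13 = 15.4%. Two higher doses: 10/12 = 83.3%. Fisher exact p = 0.0012, with the split chosen after seeing the data.
- The pooled rate is the weighted mean of these two: (2 + 10)/(13 + 12) = 48.0%.

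So the combined column is uninformative when read alone.

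**3. How strong is the dose relation?** The Cochran-Armitage statistic over active doses uses events x, group sizes n, doses d, N = 25 and p = 0.48:
- T = Σ d(x − np) = 1890(−2.36) + 3150(−1.88) + 4410(2.12) + 5040(2.12) = 9651.6
- V = p(1 − p)[Σnd² − (Σnd)²/N] = 0.2496 × (353,637,900 − 88,830²/25) = 0.2496 × 38,007,144 ≈ 9,486,583
- z = T/√V = 9651.6/3080.0 = 3.13; exact p = 0.0011 one-sided, 0.0018 two-sided.

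With placebo added at dose 0, z = 1.72 and the exact p is 0.050 one-sided, 0.092 two-sided (0.055 two-sided with rank scores). The relation weakens because placebo lies above both lower doses. The two higher doses together against placebo give Fisher p = 0.16, and the two lower against placebo give p = 0.15. The pattern is a step between 3150 and 4410 mg rather than a steady gradient.

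Exact 95% intervals are wide: 1/7, 0.4% to 57.9%; 1/6, 0.4% to 64.1%; 5/6, 35.9% to 99.6%; placebo 4/8, 15.7% to 84.3%.

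**4. Would the plan as written hide this?** Set the planned outputs beside what was reported.

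| Question | Planned or reported |
|---|---|
| Are TEAEs tabulated by dose beside placebo? | Yes: SAP Section 8 (first part of the sentence) and Section 8.1 |
| Does combined active replace those tables? | No: Section 9.1 adds it to them |
| Is the rise reported? | Yes: the synopsis states it and gives the rate in every AD cohort |
| Is placebo placed against the doses? | Yes: between Cohorts 2b and 3b |
| Is 48% against 50% offered as evidence of no difference? | No: the synopsis gives the two counts and draws no such conclusion |

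**5. Does the conclusion of good tolerability depend on pooling?** No. For AD subjects the synopsis reports no deaths, no serious events and no discontinuation due to a TEAE. It adds that each event type occurred in a single subject, apart from headache and pollakiuria. None of these statements needs a combined-active contrast.

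**The case for a change.** The strongest case for the concern does not need masking at all. The SAP is not purely descriptive: Section 7.3 pre-specifies a 90% confidence interval with acceptance limits for steady state, while the primary safety objective has no interval anywhere. The dose question is left to reading cells of about 6 subjects by eye. Exact intervals per dose and a descriptive trend summary would need no new data and would show readers how uncertain 1/7 or 5/6 is. The combined-active display is also not labelled as supportive.

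These facts are correct, but they do not amount to a defect. Section 7.3 attaches an interval to a decision rule, and no decision on safety is tied to a test. SAP Section 3.5 says openly that the sample size has no statistical basis. The counts are fully visible, and an interval from 0.4% to 57.9% tells the reader little more than 1 of 7 does. The cohorts were enrolled one after another and randomised separately, so dose is confounded with cohort and calendar time, which an active-only trend test would not remove.

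The point about the MTD endpoints is also accurate as far as Table 1 goes. But the documents openly use exposure thresholds for that objective, and adverse events and tolerability are reviewed by cohort before progression (Protocol synopsis, Study Design and Conduct; SAP Section 3.1). Tolerability by dose therefore enters the conduct of the study. Listing TEAEs by dose a second time under the MTD objective would move a table without changing a result.

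**Conclusion.** The concern does not hold. The combined-active column does flatten a contrast of 15.4% against 83.3% into 48.0%, but it accompanies dose-level tables that the same SAP sentence requires, and the synopsis reports the rise cohort by cohort. Making dose level the main safety presentation would ask for what the plan already does.

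What remains is that no safety interval or trend test is planned. Reasonable statisticians differ on whether to add one to a small descriptive Phase 1/2a study, and doing so would change no reported figure or stated conclusion.

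The figures cover AD subjects only, at 1890 to 5040 mg/day, since Cohort 5b was not conducted. Healthy-cohort rates by dose are not in the text available here and were not checked. The cohort counts are inferred from rounded percentages, although the solution is unique for group sizes of 5 to 8 and matches the reported total. All p-values and intervals here are post hoc.
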